# 9.2 Analysis Populations

*Safety population*: Subjects will be evaluable for safety if they receive at least one dose of APR-246. The safety population will be used to summarize exposure and safety parameters.

*DLT-evaluable population*: All subjects who either experience a DLT during first the 3 weeks (Cycle 1) of the study treatment or receive  $\geq$  75 % of scheduled Cycle 1 dose of APR-246 in combination with pembrolizumab and do not experience a DLT. Any individual subject who is not evaluable for DLT will be replaced by a new subject through additional subject enrollment.

*Efficacy evaluable (EE) population*: All subjects who complete at least one treatment cycle of APR-246 in combination with pembrolizumab and who have at least one post-treatment clinical response assessment. Subjects who fail to complete one treatment cycle will also be considered EE if they show clear evidence of clinically significant disease progression. The EE population will be the secondary analysis population for efficacy.

*PK population*: Subjects will be evaluable for PK if at least one post-dose sample for PK evaluation has been obtained.

*PK/Pharmacodynamic population:* All subjects who receive at least 1 dose of study drug (APR-246 pembrolizumab) and have evaluable pharmacodynamic and concentration data.

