documentation of confirmed disease progression or death (whichever occurs first).

 
OS, measured from the date of initiating study treatment to the date of death.
 
DOR, defined as the duration of CR or PR.
 

5. DCR, defined as the proportion of subjects who have BOR of CR or PR or SD (duration of SD $\ge$ 5 weeks).
6. Durable SD rate, defined as the proportion of subjects whose BOR is SD and the duration of SD is $\geq$ 23weeks.
7. CBR, defined as the proportion of subjects who have BOR of CR or PR or durable SD (duration of SD $\ge$ 23 weeks).
8. PK parameters: maximum concentration (C max ), area under curve (AUC), volume of distribution (V d ) and clearance (CL) of APR-246 when administered concurrently with pembrolizumab.
Exploratory endpoints:
Exploratory molecular analyses may include but are not limited to: gene mutations by next generation sequencing (NGS, including TP53), mRNA expression, multiplex immunohistochemistry and transcriptomics in frozen biopsies before and on therapy, multiplex flow cytometry on peripheral blood mononuclear cells (PBMCs) and multiplex cytokines in serum.
Analysis Sets: Safety Analysis Set will include all subjects who receive any amount of study drug. This will be the analysis set for all safety evaluations.
MTD Analysis Set will include all subjects who complete Cycle 1 of treatment in the safety lead-in portion of the study or discontinue early due to DLT. This will be the analysis set to determine MTD.
PK Analysis Set : All the subjects who receive at least 1 dose of APR-246 and have evaluable concentration data.

	Dharmanaduramia Analusia Catwill include all subjects who receive at least 1 does of
	Pharmacodynamic Analysis Set will include all subjects who receive at least 1 dose of study drug (APR-246 or pembrolizumab) and have evaluable pharmacodynamic data.
	PK/Pharmacodynamic Analysis Set : All the subjects who receive at least 1 dose of study drug (APR-246 or pembrolizumab) and have evaluable pharmacodynamic and concentration data.
Eligibility	Inclusion Criteria:
Criteria	
 
Signed informed consent form (ICF) and ability to comply with protocol requirements.
 
Known tumor TP53 mutation status from recent or archival sample.
 
Histologically and/or cytologically confirmed solid tumor malignancy:
 

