	The dose expansion consists of 3 cohorts. The ORRs to pembrolizumab for the patients with the 3 types of cancer, who were relapsed/refractory R/R to previous chemotherapies, were 21.1% and 22,7% for urothelial cancer and gastric/GEJ adenocarcinoma, respectively. The ORR for patients with advanced NSCLC who have previously been treated with anti-PD-1/PD-L1 therapy is expected to be negligible

(i.e. <= 20%). As such, the expected response rate to the combination therapy across indications is 20% to 30%. In order to increase the estimate precision, at least 20 evaluable patients will be included in each of the 3 cohorts.
Analysis Populations
Safety population: Subjects will be evaluable for safety if they receive at least one dose of APR-246. The safety population will be used to summarize exposure and safety parameters.
DLT-evaluable population: In the safety lead-in portion of the study, subjects who either experience a DLT during first the 3 weeks (Cycle 1) of the study treatment or receive $\geq$ 75% of scheduled Cycle 1 dose of APR-246 in combination with pembrolizumab and do not experience a DLT. Any individual subject who is not evaluable for DLT will be replaced by a new subject through additional subject enrollment.
Efficacy evaluable (EE) population: All subjects who complete at least one treatment cycle of APR-246 in combination with pembrolizumab and who have at least one post-treatment clinical response assessment. Subjects who fail to complete one treatment cycle will also be considered EE if they show clear evidence of clinically significant disease progression. The EE population will be the secondary analysis population for efficacy.
PK population: Subjects will be evaluable for PK if at least one post-dose sample for PK evaluation has been obtained.
PK/Pharmacodynamic population: All the subjects who receive at least 1 dose of study drug (APR-246 pembrolizumab) and have evaluable pharmacodynamic and concentration data.
Statistical analysis
All the statistical analysis will be detailed in the statistical analysis plan.

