### 4.0 TRIAL DESIGN

### 4.1 Overview of Trial Design

This is a phase 1/2, open-label, study to determine the safety and preliminary efficacy of APR-246 in combination with pembrolizumab in subjects with solid tumor malignancies.

In the safety lead-in part of study (phase 1), the safety and the RP2D of APR-246 will be investigated. The RP2D of APR-246 will be defined as the dose at which < 2 out of 6 subjects experience DLT during the 3-week safety assessment period after the start of APR-246 administration in combination with pembrolizumab using dose de-escalation of APR-246.

In the expansion part of the study (phase 2), both safety and efficacy for the combination therapy will be investigated in the 3 cohorts.

Study treatment may be administered on an outpatient basis. No investigational or commercial anti-tumor agents or therapies other than those described below may be administered with the intent to treat the patient's underlying malignancy.

The study will include a safety lead-in dose-finding portion followed by expansion portion. During the safety lead-in portion of the study, subjects with (non-CNS primary) solid tumor malignancies will receive pembrolizumab in combination with APR-246 in a 3 + 3 dose deescalation design.

Dosing will begin at the full dose of both drugs due to the well-established safety profiles of APR-246 and pembrolizumab, the non-overlapping mechanisms of action, and the intent to treat patients at doses shown to be effective in previous studies. Lower dose levels of APR-246 will be explored as necessary depending on observed AEs.

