The initial cohort of subjects will receive APR-246 at 4.5 g/day administered as an IV infusion on Days 1–4 in combination with pembrolizumab at the approved dose of 200 mg on Day 3 of each 21-day cycle. This cohort will enroll up to a maximum or 6 subjects. DLT will be assessed after 3 subjects have been enrolled in each respective cohort and the last enrolled subject has completed the 3-week safety assessment period (i.e., one cycle of combination regimen). A subject that discontinues therapy during Cycle 1 without DLT is considered evaluable for the purpose of safety only if at least 75% of scheduled doses of APR-246 were administered in the first cycle. At the first dose level of 4.5 g/day of APR-246, if  $\leq$  1 subject out of 3 experiences a DLT, 3 additional subjects will be enrolled. If  $\leq$  1 subject out of 6 experiences DLT, the dose level (4.5 g/day of APR-246) will be deemed the RP2D for that cohort. If  $\geq$  2 subjects out of the total 3 – 6 subjects in the cohort experience DLT, the study will continue enrollment at Dose Level -1 (4.0 g/day of APR-246) (see Table 1). If  $\leq$  1 subject out of 6 experiences DLT at this dose level, the dose level (4.0 g/day of APR-246) will be deemed the RP2D for that cohort. If  $\geq$  2 subjects out of 3 – 6 subjects at that Dose Level -1 experience DLT, the study will continue enrollment at Dose Level -2 (3.5 g/day of APR-246). If  $\leq$  1 subject out of 6 experiences DLT at this dose level, the dose level (3.5 g/day of APR-246) will be deemed the RP2D for that cohort. If  $\geq$  2 subjects out of 3 – 6 subjects at this dose level experience DLT, the trial will be halted and the Data Review Team (DRT) will consider potential future dosing modifications. No dose reductions in pembrolizumab are planned.

Dose Modification	APR-246 Dose
Starting Dose Level (DL)	APR-246 4.5 g/day 1.5 g (for first 45 minutes) + 3.0 g (for 5 hours 15 minutes)
Dose Level Reduction -1 (DL-1)	APR-246 4.0 g/day 1.33 g (for first 45 minutes) + 2.67 g (for 5 hours 15 minutes)
Dose Level Reduction -2 (DL-2)	APR-246 3.5 g/day 1.17 g (for first 45 minutes) + 2.33 g (for 5 hours 15 minutes)

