# 6.1.1 Dose-Limiting Toxicity

A DLT is defined as any of the following:

- Any of the hematological or nonhematological toxicities noted in the table below considered to be at least possibly related to APR-246 occurring during the 3-week safety assessment period after the start of APR 246 administration in combination with pembrolizumab (Cycle 1 Day 1).
- Failure to administer ≥75% of the planned dosage of APR-246 as a result of treatment-related toxicity during Cycle 1, unless reversible CNS-related effects previously described for APR-246.
- Subjects who discontinue treatment due to treatment-related toxicity.
- Greater than 4-week delay in starting Cycle 2 because of a treatment-related toxicity, even if the toxicity does not meet DLT criteria.

Dose-Limiting Toxicities	5 · · · · · · · · · · · · · · · · · · ·
Toxicity Category	Toxicity CTCAE Grade
Hematologic	Grade 4 neutropenia for ≥ 7 days
	Grade 3 or Grade 4 febrile neutropenia a
	Thrombocytopenia <25,000/mm  associated with bleeding and/or that
	requires platelet transfusion
Other nonhematologic	Any other Grade 4 or a Grade 5 toxicity
toxicity	Grade 3 toxicities lasting > 3 days excluding:
	Nausea, vomiting, fatigue and diarrhea controlled by medical
	intervention within 72 hours.
	Grade 3 rash in the absence of desquamation, no mucosal involvement,
	does not require steroids, and resolves to Grade 1 by the next
	scheduled dose of pembrolizumab.
	Grade 3 hypertension not able to be controlled by medication
	Grade 3 or above gastrointestinal perforation
	Grade 3 or above wound dehiscence requiring medical or surgical
	intervention
	Any grade thromboembolic event
	Any Grade 3 non-hematologic laboratory value if: Medical intervention is
	required to treat the subject, or the abnormality leads to hospitalization
ANC = absolute neutrophil cour	nt, CTCAE = Common Terminology Criteria for Adverse Events v5.0.
a Febrile neutropenia Grade 3 o	
	00/mm  with a single temperature of >38.3 °C (101 °F) or a sustained temperature of ≥ 38 °C
(100.4 °F) for more than one ho Grade 4 is defined as ANC < $100$	ur. )0/mm³ with a single temperature of >38.3 °C (101 °F) or a sustained temperature of ≥ 38 °C
	ur, with life-threatening consequences and urgent intervention indicated

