Only toxicities with a clear alternative explanation (e.g., due to disease progression) or transient ( $\leq$  72 hours) abnormal laboratory values without associated clinically significant signs or symptoms based on investigator determination can be deemed a non-DLT.

All subjects enrolled in the safety lead-in portion will be assessed for DLTs during the 3-week DLT assessment period of Cycle 1. Subjects who discontinue study treatment prior to completing Cycle 1 of study treatment for any reason other than DLT will be replaced.

Additionally, AEs that meet the above criteria, but occur after the DLT evaluation period will not be defined as DLTs, but will be reported as AEs/SAEs and will be reviewed across all cohorts during the study to help determine the AE profile.

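### The synopsis MTD Analysis Set keeps a subject who completes Cycle 1 below 75% of dose because of DLT-exempt CNS effects, while the DLT-evaluable population replaces the same subject

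*Combined protocol and SAP*

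**What the plan says.** Section 6.1.1 makes it a DLT to give less than 75% of "planned dosage of APR-246 as a result of treatment-related toxicity during Cycle 1, unless reversible CNS-related effects previously described for APR-246". Under-dosing caused by those CNS effects is thus not a DLT in itself.

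The plan then describes the subjects who count in two ways:

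- **DLT-evaluable population** (synopsis, Analysis Populations; section 9.2). A subject without a DLT must have received at least 75% of the "scheduled Cycle 1 dose of APR-246 in combination with pembrolizumab and do not experience a DLT". For everyone else, "Any individual subject who is not evaluable for DLT will be replaced by a new subject through additional subject enrollment".
- **MTD Analysis Set** (synopsis, Analysis Sets). This set, named as the one that determines the MTD, "will include all subjects who complete Cycle 1 of treatment in the safety lead-in portion of the study or discontinue early due to DLT". It has no dose threshold.

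Two further rules concern subjects who stop treatment. In section 4.1, the rule for a subject who stops early reads, in part, "discontinues therapy during Cycle 1 without DLT is considered evaluable for the purpose of safety only if at least 75% of scheduled doses"; the doses meant are those of APR-246. In section 6.1.1, "Subjects who discontinue study treatment prior to completing Cycle 1 of study treatment for any reason other than DLT will be replaced".

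Section 4.1 also says of the first dose level: "This cohort will enroll up to a maximum or 6 subjects". Section 9.1 sizes the lead-in at up to 18 DLT-evaluable patients. The RP2D is the dose at which fewer than 2 of 6 subjects have a DLT (section 6.1.2).

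**The concern.** The RP2D is a primary endpoint, finding the MTD is a primary objective, and the chosen dose goes to up to 100 expansion subjects. The plan gives no MTD rule apart from the fewer-than-2-of-6 count, and section 6.1.2 does not name the analysis set for that count.

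Suppose a subject completes Cycle 1 below 75% because of exempt CNS effects. Under the MTD Analysis Set the subject is one of the six and has no DLT. Under section 9.2 the subject is not one of the six, and someone else must be treated. The same data can then support two dose decisions. In an open-label lead-in, the Data Review Team would have to choose the rule with the results in view. Keeping the subject also counts someone exposed to less than the required dose as having tolerated it.

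**Working it through.** **The plan's own figure.** Three dose levels (4.5, 4.0 and 3.5 g/day, Table 1) × 6 = 18, which matches section 9.1. The 6 per level is therefore naturally 6 DLT-evaluable subjects.

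**Can the case occur?** The scheduled Cycle 1 dose at the starting level is 4 × 4.5 = 18 g, and 75% of that is 13.5 g. Losing one whole infusion leaves 13.5/18 = 75%, which still qualifies, so more must be lost. Section 6.3.2 stops the day's infusion and discards the rest if an AE lasts over 2 hours, and Table 2 lowers the subsequent dose by one level. Treatment itself continues. Take stops at 3 h on Days 1 and 2:

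- dose given by hour t (t > 0.75) = loading + maintenance × (t − 0.75)/5.25
- Day 1 at 4.5 g/day: 1.5 + 3.0 × 2.25/5.25 = 2.786 g
- Day 2 at 4.0 g/day: 1.33 + 2.67 × 2.25/5.25 = 2.474 g
- Days 3 and 4 at 3.5 g/day: 7.0 g
- total 12.26 g, or 12.26/18 = 68.1%

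The CNS event must meet no other DLT criterion and must not lead to discontinuation for toxicity, which is itself a DLT.

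**What each rule does with this subject**

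| Text | Result |
|---|---|
| Synopsis and 9.2, DLT-evaluable | No DLT and below 75%: not evaluable, replaced |
| Synopsis, MTD Analysis Set | Completed Cycle 1: included, non-DLT |
| 4.1, 75% sentence | Addresses discontinuers; silent here |
| 6.1.1, replacement sentence | Addresses discontinuers; silent here |

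**Effect on the decision.** Assume one such subject among six and an independent DLT rate p in every other subject, including a replacement. The value of p is an assumption.

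- Replaced: P(RP2D) = P(at most 1 DLT in 6) = (1−p)^6 + 6p(1−p)^5
- Kept as a non-DLT: P(RP2D) = P(at most 1 DLT in 5) = (1−p)^5 + 5p(1−p)^4

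| p | Replaced | Kept | Difference |
|---|---|---|---|
| 0.1 | 0.886 | 0.919 | 0.033 |
| 0.2 | 0.655 | 0.737 | 0.082 |
| 0.3 | 0.420 | 0.528 | 0.108 |

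Cross-check: the readings part only if exactly one of the other five has a DLT and the replacement has one too. That is 5p(1−p)^4 × p = 0.033, 0.082 and 0.108, the same differences. Enumerating the two stages of three subjects gives the same replaced values at p = 0.2 and 0.3.

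**The base of the 75%.** The plan refers to planned dosage (6.1.1), scheduled doses (4.1) and scheduled Cycle 1 dose (9.2). None says whether a Table 2 reduction within the cycle lowers the base. The 12.26 g above is 68.1% of 18 g, but 12.26/(4.5 + 4.0 + 3.5 + 3.5) = 12.26/15.5 = 79.1% of the reduced schedule. The first is not evaluable and the second is.

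**The case against.** The best defence is that the documents already lean one way. The DLT-evaluable definition is stated twice and the sample size is counted in that unit. The MTD Analysis Set appears once, in the synopsis, and not in section 9.2. Completing Cycle 1 is undefined and could mean receiving all its doses. This stands as a reason to resolve the matter in favour of section 9.2. It does not remove the conflict: the synopsis set is expressly the one for the MTD, and section 6.1.1 treats completion as not having discontinued.

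The case is also narrow, and the Data Review Team is not blind to it. All accumulated safety data are discussed at its meetings, exposure is summarised, and "Lower dose levels of APR-246 will be explored as necessary depending on observed AEs". That stands and keeps the severity low, but it does not say who is among the six. On the base, planned or scheduled dose ordinarily means the assigned regimen, so that part is a clarification.

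A reader might infer more in four ways, none supported:

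- *Sections 4.1 and 6.1.1 keep the subject as a non-DLT.* Their sentences concern subjects who discontinue and say nothing about completers.
- *The CNS exemption makes the subject evaluable.* It only says that this under-dosing is not a DLT.
- *The cap of 6 forbids a replacement.* Section 9.2 provides for additional enrolment, and 18 DLT-evaluable over three levels means 6 evaluable at each.
- *The decision changes with probability 10%, 20% or 30% (up to 51% with two such subjects at a 30% rate).* Those figures apply only once exactly one DLT has been seen among the others.

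**Conclusion.** Wrong as written, minor severity: two stated rules give different denominators for a primary-endpoint decision, and no text says which governs. The explicit conflict is between the synopsis MTD Analysis Set and the DLT-evaluable population; sections 4.1 and 6.1.1 merely fail to resolve it. The size is about 3, 8 and 11 percentage points in the chance of declaring the RP2D, at assumed DLT rates of 10%, 20% and 30%. It rests on there being one such subject among six, on independent DLTs, and on a replacement who is fully evaluable. How often the case would arise cannot be judged from the documents.

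**What to change.** 1. Define the MTD Analysis Set as the DLT-evaluable population of section 9.2 for lead-in subjects, and name that set in the fewer-than-2-of-6 rule.
2. State in sections 4.1 and 6.1.1 that any subject without a DLT who receives less than 75% of the scheduled Cycle 1 dose, including because of exempt CNS effects, is replaced.
3. State the maximum of 6 per dose level as 6 DLT-evaluable subjects.
4. Use one term for the base everywhere: the scheduled Cycle 1 dose is four times the cohort's assigned daily dose (18 g at 4.5 g/day) and is not lowered by Table 2 reductions.
5. Optionally, list at each Data Review Meeting the number of subjects per dose level who fell below 75% for exempt CNS effects, beside the DLT count. Infusion start, stop and rate-change times are already recorded (section 6.1).

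Keeping these subjects as non-DLTs would also give a single rule. But it would override the 75% threshold that the plan states twice, and it would make a toxic dose easier to pass (42.0% to 52.8% at a 30% DLT rate, with one such subject). Replacement is the safer choice.

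The cost is wording, plus possibly an occasional replacement subject, which section 9.2 already provides for.

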# 9.3 Data Summaries

Generally, all the continuous variables will be summarized using n (number of subjects with available data), mean, standard deviation (StDev), median, and range (minimum and maximum). Categorical data will be summarized by frequency and percentage. Time to event data will be analyzed using Kaplan-Meier method, and the number and percentage of events, or censored, the first quartile at 25%, median with 95% confidence, and third quartile at 75% of survival time will be presented. The survival rate at the 3, 6, 9, and 12 months, and then 2, 3 and 5 years will be presented. All the study data will be listed.

The following general study data, demographic, baseline characteristics and disease history will be summarized:

- Subject disposition
- Protocol deviation
- Demographics
- Cancer disease diagnosis and history
- Prior cancer treatments
- Medical history
- Prior/concomitant medications

Safety data including AEs, vital signs, laboratory data, ECG, physical exam, ad ECOG performance status will be summarized in the safety population. AEs will be coded using MedDRA and graded using NCI-CTCAE v5.0 severity grade.

The efficacy endpoints in the safety lead-in portion will be listed only. In the expansion phase, all the rates will be summarized with 95% exact CI (Clopper and Pearson) by cohorts. The time to event data will be analyzed using Kaplan-Meier method and the corresponding survival plots will be produced.

To assess any DDI between APR-246 and pembrolizumab, the primary PK parameters of APR-246 will be compared graphically and via descriptive statistics with historical data using the PK analysis set. If warranted, additional analyses may be performed. A popPK model for APR-246 will be developed. The model will be parameterized in terms of CL and Vd.

The effect of APR-246-pembrolizumab combination therapy on soluble, tissue, genetic and/or imaging biomarkers will be summarized using descriptive statistics using the PK/pharmacodynamic analysis set. PK/pharmacodynamic relationships will be explored graphically and may be investigated by model-based analyses.

Descriptive statistics/results from exploratory molecular analyses will be written and may include but are not limited to: TP53 variant allele frequency by next-generation sequencing (NGS), p53 immunohistochemistry, mutations in other genes by NGS, RNA expression.

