#### APR-246

APR-246 is administered as a 6-hour IV infusion daily on Days 1–4 of each 21-day cycle. APR-246 fixed dose is 4.5 g. APR-246 is administered in a 2-step infusion:

- Step 1: Loading dose of 1.5 g for the first 45 minutes (± 2 min)
- Step 2: Maintenance dose of 3 g over 5 hours 15 minutes (± 30 min)

The dose of APR-246 may be reduced (please consult Section 4.1 and Table 1) or treatment interrupted if the subject develops AEs.

APR-246 vials are to be stored at 2 – 8°C (35.6 – 46.4°F). At the pharmacies and at the study centers, the prepared APR-246 study product (diluted in sodium chloride solution) is to be stored at no greater than 25°C. The infusion should be completed within 24 hours from the time of preparation.

Detailed instructions on vial concentration, preparation and dispensing can be found in the Pharmacy Binder. The infusion timing, including start/stop times and the time of rate change, must be recorded.

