#### 8.5 Pharmacokinetics

Plasma concentrations of APR-246 will be measured in Cycle 1 and again in Cycle 3, at the timepoints provided in Table 5.

APR-246 plasma collection timepoints a	D1	D2	D3	D4
Prior to APR-246 infusion	×	×	×	×
At the end of APR-246 infusion	×		×	
1 hour after the end of APR-246 infusion	×		×	
3 hours after the end of APR-246 infusion	×			

**Table 5.** PK Blood Sampling Timepoints for APR-246 in Cycle 1 and Cycle 3

a A window of ±15 min applies to each time point.

The data will be evaluated using population pharmacokinetics (see section below).

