# 9.4 Pharmacokinetic Analysis

# Pharmacokinetic Analysis

The DDI between APR-246 and pembrolizumab will be evaluated using popPK methods. The existing popPK model for APR-246 will be used to compare the observed plasma concentrations of APR-246 in presence of pembrolizumab with the predicted plasma concentrations assuming no DDI (visual predictive check). Additionally, the PK analysis dataset from this study will be integrated with the existing popPK dataset and the effect of pembrolizumab on APR-246 PK parameters will be tested as covariate in the model.

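### The APR-246/pembrolizumab interaction is judged mainly against external data, and the pooled covariate's coding is unstated, although samples already scheduled give PD-1/PD-L1-naive subjects their own pembrolizumab-free control

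*Combined protocol and SAP*

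**What the plan says.** The PK profile of APR-246 given with pembrolizumab is a secondary objective (Section 3.2, item 8). The interaction is addressed in three ways:

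- **Section 9.3:** "the primary PK parameters of APR-246 will be compared graphically and via descriptive statistics with historical data". No ratio, interval or no-effect bound is given.
- **Section 9.4, first part:** a visual predictive check sets observed APR-246 concentrations against predictions from the existing population PK model, assuming no interaction.
- **Section 9.4, second part:** after pooling with the existing dataset, "the effect of pembrolizumab on APR-246 PK parameters will be tested as covariate in the model". How the covariate is coded is not stated.

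On sampling, Section 8.5 says: "Plasma concentrations of APR-246 will be measured in Cycle 1 and again in Cycle 3, at the timepoints provided in Table 5". On Day 1, Table 5 has pre-infusion, end-of-infusion, 1-hour and 3-hour samples. Day 3 has the same set without the 3-hour sample. Days 2 and 4 have a pre-infusion sample only.

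On dosing, "APR-246 is administered as a 6-hour IV infusion daily on Days 1–4 of each 21-day cycle" (Section 6.1). Pembrolizumab is placed on Day 3 with a one-day window either side, and also ahead of that day's APR-246 infusion (Sections 6.1 and 7.2.1.1).

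On earlier exposure, Section 5.1 bars prior anti-PD-1/PD-L1 therapy in the gastric/GEJ and urothelial cohorts and requires it in the NSCLC cohort. It neither bars nor requires it in the lead-in. The only washout rule (Section 5.2, item 10) concerns investigational products.

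**The concern.** Every subject here is to receive pembrolizumab, and the existing model is used as the reference without an interaction. A comparison between this study and earlier ones therefore carries the pembrolizumab effect together with everything else that differs between them. A covariate that takes one value per subject or per study has the same problem. A between-study difference could be reported as an interaction, or could offset a real one and hide it.

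The schedule offers a contrast free of this problem, and no analysis names it. In a subject never exposed to a PD-1/PD-L1 antibody, Cycle 1 Day 1 is a true pembrolizumab-free occasion, because the earliest allowed pembrolizumab day is Day 2. Cycle 3 Day 1 repeats the same four sampling times, is also the first APR-246 dose of its cycle, and falls while pembrolizumab is present.

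**Working it through.** The plan gives no sample size, precision or bound for this question, so there is no design figure to reproduce. The one stated PK figure that matters here can be checked. The 22-day half-life in Section 2.4 with 21-day dosing gives accumulation 1/(1 − 2^(−21/22)) = 2.07, against the stated 2.1-fold.

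**1. Is pembrolizumab present on the second occasion?** Take single-exponential decline, doses on Days 3 and 24, and the level just after the first dose as one unit. Cycle 3 Day 1 is Day 43:

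2^(−40/22) + 2^(−19/22) = 0.284 + 0.550 = 0.83 units, against 0 on Cycle 1 Day 1 in a naive subject.

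**2. What of a subject coming off steady-state pembrolizumab?** The residual on Cycle 1 Day 1, d days after the last dose, is 2.066 × 2^(−d/22). By Cycle 3 Day 1, 42 days later, it has fallen by a factor of 2^(−42/22) = 0.266.

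| d (days) | Cycle 1 Day 1 | Cycle 3 Day 1 | Difference |
|---|---|---|---|
| naive | 0 | 0.83 | 0.83 |
| 21 | 1.07 | 0.83 + 0.28 = 1.12 | 0.05 |
| 42 | 0.55 | 0.83 + 0.15 = 0.98 | 0.43 |

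At 84 and 110 days the Day 1 residual is 0.15 and 0.06. Recent exposure thus removes most of the contrast and pulls the ratio towards 1. For other PD-1/PD-L1 antibodies the documents give no half-life.

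**3. How many subjects have a clean control?** At least 20 evaluable in each of three cohorts (Section 9.1). Two cohorts must be naive: 2 × 20 = 40 of at least 60 expansion subjects, before attrition to Cycle 3.

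**4. Between-study bias.** The documents give no APR-246 variability, so assume a between-subject CV of 30 to 50%, with σ = √ln(1 + CV²). Suppose there is no interaction, but the historical population differs by 10% for other reasons. Treat the reference as fixed, with n = 60. With δ = ln(1.1)/(σ/√60), the chance that a 90% interval excludes 1 is Φ(δ − 1.645) + Φ(−δ − 1.645).

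- CV 30%: σ = 0.294, δ = 0.0953/0.0379 = 2.51, chance 81%.
- CV 50%: σ = 0.472, δ = 0.0953/0.0610 = 1.56, chance 47%.

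The nominal figure is 10%. For a 20% difference the range is 91 to 100%. Section 9.3 plans no interval, so these figures show how far such a comparison can mislead; they are not the error rate of a planned test.

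**5. Precision.** Assume a between-subject CV of 25 to 40% and a within-subject CV of 10 to 20%. The variance ratio, historical (reference fixed) to paired, is (σB² + σW²)/(2σW²). The 90% half-width factors at n = 20 use t = 1.729.

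| CV between/within | Variance ratio | Historical | Paired |
|---|---|---|---|
| 30% / 15% | (0.0862 + 0.0223)/(2 × 0.0223) = 2.4 | 1.136 | 1.085 |
| 25% / 20% | (0.0606 + 0.0392)/(2 × 0.0392) = 1.3 | 1.130 | 1.114 |
| 40% / 10% | (0.1484 + 0.00995)/(2 × 0.00995) = 8.0 | 1.166 | 1.056 |

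When the two CVs are equal the ratio is 1. If the within-subject CV is the larger, the paired interval is wider. At n = 40 the paired 90% interval around a true ratio of 1 is 0.95 to 1.06, 0.93 to 1.08 or 0.90 to 1.12 for a within-subject CV of 15, 20 or 30%.

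**6. Why Day 3 against Day 1 is only supportive.** Day 3 carries APR-246 over from Days 1 and 2. The interval-AUC factor is (1 − r³)/(1 − r), with r = 2^(−24/h). For an assumed APR-246 half-life h of 4, 6, 8 or 12 hours the excess is 2, 7, 14 or 31%. Day 3 also lacks the sample taken "3 hours after the end of APR-246 infusion".

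**The case against.** The strongest reply is that Section 9.4 relies on population PK methods, not only on a historical comparison. If its pembrolizumab covariate is time-varying, the model already uses Cycle 1 Day 1 as the subject's own control. That stands as a possibility: the text does not say that coding is by study, so a reader should not infer that the question is answered by historical data alone. It does not say the opposite either, and the confounded version remains open. Section 9.3's allowance for further analyses if warranted, and the Synopsis's deferral of detail to the statistical analysis plan, prespecify nothing on this point.

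A reader might also infer that the schedule gives every subject a pembrolizumab-free control. The documents do not support that: NSCLC subjects must have been treated with a PD-1/PD-L1 antibody, lead-in subjects may have been, and no washout is set for marketed agents. An unrestricted Cycle 3 against Cycle 1 ratio would be diluted, as step 2 shows.

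The actual differences from the historical data are largely unknown here. Headings in Section 2.3 show earlier studies in haematologic malignancies, ovarian cancer and myeloid neoplasms, but their content is not readable. Differences in renal function, infusion scheme or assay cannot be asserted, and the existing model may adjust for some of them.

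The within-subject contrast has its own weaknesses: fixed order, restriction to subjects still treated at Cycle 3, and APR-246 dose changes. Finally, the Synopsis presumes no interaction from disparate metabolism, and no decision rule depends on this analysis. That limits the weight of the point, but a statement of no interaction still needs an estimate with an interval.

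**Conclusion.** The point holds in a limited form. Section 9.3 and the predictive check in Section 9.4 rest on external data, and the coding of the covariate in Section 9.4 is unspecified. An own control is already sampled but not named in any analysis. It is assured in at least 40 expansion subjects.

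The case rests on bias. Under the assumed CVs, a 10% between-study difference would look like an interaction in roughly half to four-fifths of trials at n = 60. The within-subject contrast removes between-study differences, but not time or selection effects. A large precision gain should not be inferred: the variance ratio runs from about 1.3 to 8.0 over the assumed ranges and can fall below 1 outside them. Nor does anything here suggest that an interaction exists. As this supports a secondary objective, the change is worth making but is of moderate weight.

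**What to change.** In Section 9.4, with 9.3 aligned:

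1. Code pembrolizumab as a time-varying covariate by actual infusion time (zero on Cycle 1 Day 1 in naive subjects), with a separate study effect.
2. Report the within-subject geometric mean ratio with 90% CI for dose-normalised APR-246 exposure at matched times, Cycle 3 Day 1 against Cycle 1 Day 1. Make anti-PD-1/PD-L1-naive subjects the main set. State how many reach Cycle 3 and how many had an APR-246 dose change.
3. Use Cycle 1 Day 3 against Day 1 only as support, model-based or corrected for carry-over, and only where actual times show that pembrolizumab was given first.
4. Classify the other subjects by agent and date of the last prior anti-PD-1/PD-L1 dose.
5. Keep the historical comparison as descriptive.

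The pembrolizumab window and the requirement that it precede the Day 3 APR-246 dose conflict, since the window admits Day 4. These passages must be reconciled.

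The cost is analysis text, a little more analysis work, and a check that the eCRF captures pembrolizumab infusion times and the last prior PD-1/PD-L1 dose. No new samples are needed. Fixed order and attrition before Cycle 3 remain as limits to state.
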